16.3. OTHER EFFICACY

The other efficacy analyses will be performed for the mITT population.

- Moderate/severe COPD exacerbation frequency over 24 weeks.
- Time to first moderate/severe COPD exacerbation over 24 weeks.
- Study withdrawal before scheduled visit at 24 weeks.
- Change from baseline to post-baseline EQ-5D-5L at Week 12
- HRU over 24 weeks
- Change from baseline FEV₁ to average FEV₁ AUC_{6-12h} at Week 12
- Ensifentrine concentrations following sparse PK sample collection at Weeks 6, 12 and 24
- Patient genotype/phenotype including but not limited to cytochrome P-450 (CYP)2C9 and CYP2D6 metabolic activity
- Interleukin (IL)-6, IL-8 and C-reactive protein at Weeks 12 and 24
- E-RS responder analysis
- Morning trough FEV₁ responder analysis

16.3.1. OTHER EFFICACY VARIABLES & DERIVATIONS

16.3.1.1. COPD exacerbation

COPD exacerbations are collected on the “COPD Exacerbation” page of the eCRF and severity will be derived separately using data collected in the eCRF and as per the criteria specified in section 11.6.1. of the study protocol.

Site must enter at least 2 major symptoms, or one major symptom and one minor symptom AND meet the severity criteria below, considered as a moderate or severe exacerbation of COPD.

The severity of the COPD exacerbation will be calculated as per the following:

Moderate: Worsening symptoms of COPD requiring a minimum of three days of treatment with oral/systemic corticosteroids and/ or antibiotics.

Severe: Worsening symptoms of COPD requiring in-patient hospitalization.

16.3.1.2. EQ-5D-5L

Quality of Life (QoL) was assessed using the EQ-5D-5L questionnaire. This questionnaire

consists of 5 domains: mobility, self-care, usual activities, pain/discomfort and anxiety/depression with 5 possible responses from 1 (no problem) to 5 (unable). The sixth item, referred to as a visual analogue scale (VAS) score, is an index score to self-rate health from 0 (worst) to 100 (best). Each of the 5 domains will be summed through weighing system into a health index. The health index and VAS score will be analysed and listed and 5 domains will be only listed. It is not possible to have missing items in the questionnaire, as the data are collected in an electronic tablet which doesn't allow patients to skip between items. The weighting system is described in APPENDIX 6 of the SAP.

16.3.1.3. HRU

HRU is measured by the following events: unscheduled visits to a physician office, visits to urgent care, visits to emergency department and hospitalizations for any cause and/or related to COPD and visits/contact due to COPD exacerbation. These will be recoded on the Log Form and "COPD Exacerbation" pages of the eCRF, respectively .

16.3.1.4. Genotype/phenotype

Genetics analysis is described in section 18 of the SAP.

16.3.1.5. Patient Perception Survey

At the follow-up contact each patient will fill in a survey on their perception of what drug they were on. Data recorded on "Patient Perception Survey" page of the eCRF will be listed and summarized by treatment group for the following categories:

- Patients who correctly guessed their drug
- Patients who incorrectly guessed their drug
- Patients who were unsure of their drug

16.3.1.6. FEV₁ AUC_{6-12h}

Average FEV₁ AUC_{6-12h} is calculated as described in section 16.1.1.1 of the SAP.

16.3.1.7. E-RS total score responder

E-RS total score responder is defined as a decrease from baseline in the week mean total of E-RS score greater than or equal to 2.

16.3.1.8. Morning trough FEV₁ responder

Morning trough FEV₁ responder is defined as an increase from baseline in the Morning trough FEV₁ greater than or equal to 100 mL.

16.3.2. MISSING DATA METHODS FOR OTHER EFFICACY VARIABLES

For EQ-5D-5L missing data will be imputed using imputation described in section 16.2.2.3 of the SAP and FEV₁ AUC_{6-12h} missing data will be imputed using imputation described in section 16.2.2.1 of the SAP. Morning trough FEV₁ responder missing data will be handled as described in sections 16.2.2.2 of the SAP. E-RS total score responder missing data will be imputed similar to the SGRQ total score responder analysis as described in sections 16.2.2.3 of the SAP.

16.3.3. ANALYSIS OF OTHER EFFICACY VARIABLES

Change from baseline to average FEV₁ AUC_{6-12h} will be analyzed using ANCOVA approach and missing data will be imputed using imputation, as described in sections 16.1.3 and 16.2.2.1 of the SAP, respectively.

[figure not shown]
Model assumptions will be tested and solved, if failed, as per section 16.1.3 of the SAP.

The number of moderate or severe COPD exacerbations will be analyzed using a negative binomial model adjusting for treatment, region, actual background medication strata and actual smoking strata, as well as using log study time (years) as an offset. For study time, Visit 5 will be taken into account for completer patients, and End of Study visit or last contact date for withdrawal patients. The treatment difference from the negative binomial model will be expressed as an annualized risk ratio. The data will also be summarized by treatment group over duration of the study period.

Time to first moderate or severe COPD exacerbation during the study period will be presented as per following:

- Primary approach: Analyzed using the log-rank test, stratified by region, actual background medication strata and actual smoking strata. Summary of number of patients with events and number of patients censored will be summarized. Outcome visualized using a Kaplan-Meier plot.
- Sensitivity analysis: Analyzed using Cox proportional hazards Regression model stratified by region, background medication strata and smoking strata. Patients without exacerbations will be censored at last day in the treatment period, including period of recording after possible treatment withdrawal. The treatment difference in the Cox model will be expressed as a hazard ratio.

Testing proportional hazard assumptions:

1. Check that the covariates are independent of each other through proc phreg in SAS software.
2. Check that the hazard (hazard ratio) is independent of time through $\log(-\log(\text{survival}))$ vs $\log(\text{time})$ plot and an interaction test for treatment times $\log(\text{time})$.

The health index and VAS score for EQ-5D-5L questionnaire will be analyzed using ANCOVA approach, as described in section 16.1.3 of the SAP, with data imputation described in section 16.2.2.3 of the SAP.

HRU over 24 weeks will be summarized for each event and for overall count.

Analysis for the genetics data is described in section 18 of the SAP.

Sensitivity analysis of subgroup analysis may be considered following results of the patient perception survey. The survey will be summarized to investigate if there are any signs of breaching of the blind related to the appearance of study medication.

Proportion of E-RS total score responders will be analyzed by means of a logistic regression model with fixed effects for treatment, region, actual background medication strata and actual smoking strata at baseline and baseline E-RS total score as covariate. Missing data will be imputed as described in sections 16.2.2.2 and 16.2.2.3.

Proportion of responders, with an improvement from baseline in Morning trough FEV_1 of 100 mL or more will be analyzed using a logistic regression model with fixed effects for treatment, region, actual background medication strata and actual smoking strata at baseline and baseline Morning trough FEV_1 as covariate. Missing data will be imputed as described in sections 16.2.2.2 and 16.2.2.3.

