rescue medication use. Permitted rescue and background medications and the condition of their use during the study are described in Section 6.7.2. Prohibited medications and the prohibited time intervals prior to Screening are described in Section 6.7.3.

Patients completing the run-in period and meeting all entry and Randomization Criteria will be randomized. The two different stratification factors will be applied at randomization. Details on blinded study medication and administration are provided in Section 6. The Study Schematic is shown in Section 1.2.

During the treatment period, patients will complete all assessments and procedures as outlined in the Schedule of Activities (SoA, Section 1.3) for 24 weeks. Patients completing treatment will complete a Follow-up within 4 to 10 days of the last scheduled study visit.

Patients meeting the withdrawal criteria during the study or who withdraw from the study for other reasons will be discontinued and requested to complete the Early Termination/Withdrawal Procedures and complete a Follow-up within 4 to 10 days of the Early Termination/Withdrawal Visit.

Patients who permanently discontinue double blind study medication may remain in the study and follow the assessments and procedures as noted in Section 7.2.

Number of Investigators and Study Centers

Approximately 151 Investigators and study centers are expected to participate in this study.

Number of Patients

Approximately 800 randomized patients are planned.

Treatment Groups and Duration

Randomization will be stratified by two different factors: background maintenance LAMA or LABA therapy use (yes or no) and cigarette smoking (current or former). Patients will be randomized active to placebo 5:3 for 24 weeks. The background therapy stratum will be capped at 50%. Patients in the background therapy stratum are expected to continue their background maintenance LAMA or LABA therapy daily throughout the duration of the study, with the exception of withholding 24 or 48 hours prior to spirometry as previously described.

The approximately 800 patients meeting the Randomization Criteria will be randomized to receive the following treatments in a 5:3 ratio:

Treatment Arm 1: Ensifentrine Nebulized Suspension; 3 mg BID

Treatment Arm 2: Ensifentrine Placebo Nebulized BID

Overall, 500 patients will be randomized to ensifentrine and 300 patients will be randomized to placebo.

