| Efficacy Assessments and Associated Procedures | V0 | | V1 | V2 | V3 | V4 | V5 | | | | |
| Patient Contact Day Prior to Spirometry Visits ⁸ | | | X | X | X | | X | | | | X |
| COPD Exacerbation Assessment | | | X | X | X | X | X | X | | | X |
| Spirometry Training ⁹ | X | | X | X | X | | X | | | | |
| Spirometry (pre-dose) ¹⁰ | | | X | X | X | | X | | | | |
| Spirometry 0-4 hours post dose ¹⁰ | | | X | X | | | X | | | | |
| Spirometry 0-12 hours post dose ¹⁰ | | | | | X | | | | | | X |
| Health Outcomes ¹¹ | | | | | | | | | | | |
| SGRQ | | | X | X | X | | X | | | | |
| EQ-5D-5L | | | X | | X | | | | | | |
| BDI | | | X | | | | | | | | |
| TDI | | | | X | X | | X | | | | |
| Healthcare Utilization Assessment | X | | X | X | X | X | X | X | X | X | X |
| Patient Perception Survey | | | | | | | | | | | X |

Table 3: Schedule of Activities

| Study Assessments and Procedures | Screening 1 day Clinic Visit ¹ | Run-in Period 28 Days ± 4 Days Run-in | Procedures for Patients Completing 24-Weeks of Treatment | | | | | | | Procedures for Early Term/Withdrawal | | | |
|---|---|--|--|------------------------------------|-------------------------------------|-----------------------|-------------------------------------|--------------------------------------|------------------------------------|--------------------------------------|--|----------|--|
| | | | Day 1 (Rand) Clinic Visit ¹ | Week 6 Clinic Visit ^{1,2} | Week 12 Clinic Visit ^{1,2} | Week 18 Phone Contact | Week 24 Clinic Visit ^{1,2} | Follow up Phone Contact ³ | Early Term/Withdrawal ⁴ | Follow up Phone Contact ³ | | | |
| Issue eDiary to Patients Eligible to Enter Run-in | X | | V1 | V2 | V3 | V4 | V5 | | | | | | |
| Assess eDiary and E-RS Compliance (E-RS/EXACT-PRO will be on eDiary) ¹² | | | X | X | X | X | X | X | | | | X | |
| Collect eDiary | | | | | | | | X | | | | X | |
| Safety Assessments | | | | | | | | | | | | | |
| Vital Signs ¹³ | X | | X | X | X | | | X | | | | X | |
| 12-Lead ECG (pre-dose) ¹⁴ | X | | X | X | X | | | X | | | | X | |
| 12-Lead ECG (1.5 hours post dose) ¹⁴ | | | X | X | X | | | X | | | | X | |
| Physical Examination | X | | | | | | | | | | | | |
| AE Assessment | | | X | X | X | X | X | X | | | | X | |
| Laboratory Assessments | | | | | | | | | | | | | |
| Laboratory Tests Haematology, Chemistry (non-fasting), Pregnancy Test (serum) ¹⁵ | X | | X | | | | | X | | | | X | |
| Urine Pregnancy Test for Women ¹⁵ | | | X | X | | | | | | | | | |

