3.2.3 Other Endpoints

- Moderate/severe COPD exacerbation frequency over 24 Weeks (this individual study and pooled with data from study RPL554-CO-301).
- Time to first moderate/severe COPD exacerbation over 24 Weeks (this individual study and pooled with data from study RPL554-CO-301).
- Study withdrawal before 24 Weeks.
- EuroQol-5-Domain Questionnaire (EQ-5D-5L) at Week 12 (change from baseline).
- Healthcare Resource Utilization (HRU) over 24 Weeks.
- Average FEV₁ AUC_{6-12h} post-dose at Week 12 (change from baseline).
- Ensifentrine concentrations (sparse sample collection) at Weeks 6, 12, and 24.
- Patient genotype/phenotype including but not limited to cytochrome P-450 (CYP)2C9 and CYP2D6 metabolic activity.
- Interleukin (IL)-6, IL-8, and C-reactive protein at Weeks 12 and 24.

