7.2.1 Reduced Assessments

The patient continues to follow the SoA (Section 1.3) and completes only the following assessments:

- Spirometry
- SGRQ
- COPD exacerbation
- AE
- Concomitant medication

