8.3.3 Health Outcomes

The schedule for all health outcomes assessments are provided in the SoA (Section 1.3).

During Study Visits

All patient reported outcomes administered during study visits should be administered at the beginning of a study visit before any physical activity or spirometry, except for Healthcare Utilization assessment, which can be done at any point during the visit. The following is the recommended order *as applicable for a given visit*:

- mMRC
- SGRQ
- EQ-5D-5L
- Baseline/Transitional Dyspnea Index (BDI)/TDI

8.3.3.1 *St. George's Respiratory Questionnaire*

The SGRQ Patient Reported Outcome (PRO) measure is designed to assess health-related quality of life in patients with COPD in terms of symptoms, daily activity limitation, and psychosocial well-being (Jones, 1991). The SGRQ is completed by the patient.

8.3.3.2 *EuroQol-5-Domain Questionnaire*

The EQ-5D-5L questionnaire is a standardized instrument designed to measure health utility in terms of mobility, self-care, usual activities, pain/discomfort, and anxiety/depression (Szende, 2014). The EQ-5D-5L questionnaire is completed by the patient.

8.3.3.3 *Baseline Dyspnea Index/Transitional Dyspnea Index*

The BDI is used to measure the severity of dyspnea in patients at baseline (Mahler, 1984). Mahler also developed the TDI which measures changes in patient dyspnea from baseline. The instruments are scored based on ratings for functional impairment, magnitude of task, and magnitude of effort. The BDI and TDI are administered by site staff via patient interview.

8.3.3.4 *Healthcare Utilization*

All unscheduled visits to a physician office, visits to urgent care, visits to emergency department, and hospitalizations for any cause and/or related to COPD will be recorded in the eCRF. In addition, visits and contacts that are due to a COPD exacerbation will be assessed at each clinic visit and recorded in the exacerbation form of the eCRF.

8.3.3.5 *Patient Perception Survey*

At the Follow-up contact, the study site will survey each patient regarding patient perception of their study treatment assignment.

At Home

8.3.3.6 *Evaluating-Respiratory Symptoms Questionnaire*

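### Healthcare resource use over 24 weeks is summarised as event counts with no time at risk, although its observation can end before Week 24 for some patients

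*SAP*

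**What the plan says.** Protocol 3.2.3 lists "Healthcare Resource Utilization (HRU) over 24 Weeks" among the other endpoints, in support of the objective on health utility and resource use. SAP 16.3.1.3 defines the events as unscheduled physician, urgent care and emergency visits, together with "hospitalizations for any cause and/or related to COPD and visits/contact due to COPD exacerbation". It names two sources, a log form and the exacerbation page of the eCRF.

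The analysis is one sentence in SAP 16.3.3: "HRU over 24 weeks will be summarized for each event and for overall count". The missing-data section for other endpoints (SAP 16.3.2) does not mention HRU. SAP 16.3 places these analyses in the mITT population, so patients with short follow-up are included.

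In the same section, exacerbation counts go into a negative binomial model "as well as using log study time (years) as an offset". Study time there ends at Visit 5 for completers and at the End of Study visit or last contact for withdrawals.

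On collection, the Schedule of Activities (Protocol 1.3) marks the healthcare utilisation assessment at visits and contacts, including early termination. Patients who leave the study are asked to "complete a Follow-up within 4 to 10 days of the Early Termination/Withdrawal Visit", and no contact is scheduled after that. Patients who stop study medication should ideally keep their clinic visits (Protocol 7.2). Under the first fallback, 7.2.1, "The patient continues to follow the SoA (Section 1.3) and completes only the following assessments". Neither that list nor those in 7.2.2 and 7.2.3 includes healthcare utilisation. All three keep the COPD exacerbation assessment.

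**The concern.** A count over 24 weeks has a clear meaning only if every patient is observed for 24 weeks or the shorter observation is accounted for. Here it can be shorter by two routes: leaving the study, and moving to a reduced option in which only the exacerbation-related part of HRU is still asked about. Without a denominator, weeks in which nobody asked add nothing to the count, just as weeks without healthcare use do.

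Two things follow. The level of use in each arm is understated. If the arms differ in how many patients are lost, or how early, a reader who sets the two counts side by side sees a contrast that partly reflects follow-up. The SAP recognises this for exacerbations and gives no reason for treating HRU counts differently.

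**Working it through.** **Inputs.** The plan states no HRU rate and no expected withdrawal rate by arm, so there is no HRU figure to reproduce. The only related number is in Protocol 9.2: more patients may be randomised if withdrawal at 24 weeks exceeds 25% overall. That is a trigger, not an expected rate. Allocation is 500:300 (Protocol 1.1). All arm-specific losses below are assumptions.

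**Step 1: share of 24 weeks captured.** Let d be the share of an arm whose HRU capture stops early, and f the mean fraction of 24 weeks captured in those patients. The captured share is c = 1 − d(1 − f). If losses are spread evenly over the period, f = 0.5 and c = 1 − d/2. With equal true use throughout, the apparent ensifentrine/placebo ratio of counts per patient is c(ensifentrine)/c(placebo).

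| d, ensifentrine / placebo | f | c, ensifentrine / placebo | Apparent ratio (true 1.00) |
|---|---|---|---|
| 10% / 15% | 0.5 | 0.950 / 0.925 | 1.03 |
| 10% / 20% | 0.5 | 0.950 / 0.900 | 1.06 |
| 10% / 25% | 0.5 | 0.950 / 0.875 | 1.09 |
| 25% / 25% | 0.5 | 0.875 / 0.875 | 1.00 |
| 20% / 33.3% | 0.5 | 0.900 / 0.833 | 1.08 |
| 17.5% / 37.5% | 0.25 | 0.869 / 0.719 | 1.21 |

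The last three rows hold overall loss at 25%, for example (5 × 20 + 3 × 33.3)/8 = 25. With 25% in both arms the ratio is undistorted, but each level is understated by 12.5%. In the 20%/33.3% row, a true ratio of 0.80 would appear as 0.80 × 1.08 = 0.86.

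**Step 2: timing alone.** If 10% are lost after a tenth of the period, c = 1 − 0.10 × 0.9 = 0.910. If 15% are lost halfway, c = 1 − 0.15 × 0.5 = 0.925. The arm with fewer losses then shows the lower count.

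**Step 3: leavers who use more care.** Protocol 11.6.7 ends study treatment after a second exacerbation or one needing hospital admission, so leaving may be related to HRU. Take 20%/33.3% loss and f = 0.5, and let leavers use care at k times the stayers' rate before leaving, with the same k in both arms. In units of a stayer's 24-week use:

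- count per patient = (1 − d) + d·f·k
- rate = count / c
- true 24-week use = (1 − d) + d·k if the excess persists, or (1 − d) + d(f·k + 1 − f) if it ends on leaving.

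| k | Count ratio | Rate ratio | True ratio, excess persists | True ratio, excess ends |
|---|---|---|---|---|
| 1 | 0.900/0.833 = 1.08 | 1.00 | 1.00 | 1.00 |
| 2 | 1.000/1.000 = 1.00 | 0.93 | 1.200/1.333 = 0.90 | 1.100/1.167 = 0.94 |
| 4 | 1.200/1.333 = 0.90 | 0.83 | 1.600/2.000 = 0.80 | 1.300/1.500 = 0.87 |

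The rate ratio is the count ratio divided by 1.08. In each row the count ratio lies above the truth, so the arm with more loss is shown with less use than it had. Whether that arm appears lower or higher than the other changes at k = 2. The rate is nearer the truth except at k = 4 with an excess that ends, where the two errors are similar (0.90 and 0.83 against 0.87). A rate does not remove informative dropout.

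**The case against.** The strongest case against the point is that HRU is a descriptive endpoint outside the testing hierarchy (SAP 7.4), with no model, test or claim attached. SAP 9.1 already shows study and medication withdrawals by arm with Kaplan-Meier plots and a log-rank test, so unequal follow-up will be visible. Table layouts sit in a shells document not available here (SAP 8), which may add denominators or percentages. This limits the importance of the point. It does not supply a time at risk in the SAP text.

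Three stronger readings are tempting, and the documents do not support them.

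- A reader might infer that the arm with more discontinuation must look lower, or cheaper. Steps 2 and 3 show that the apparent direction depends on timing and on leavers' earlier use. No costs are analysed.
- A reader might infer that HRU capture stops when study medication stops. Protocol 7.2 prefers continued clinic visits, at which HRU is scheduled. Under the reduced options the exacerbation component can continue: all three lists keep that assessment, and under Protocol 8.3.3.4 "visits and contacts that are due to a COPD exacerbation will be assessed at each clinic visit" and entered on the exacerbation form. Other hospital admissions may surface as serious adverse events, but SAP 16.3.1.3 does not name those as an HRU source. The gap under reduced follow-up is therefore mainly use unrelated to exacerbations, in a group of unknown size.
- A reader might take 25% as the expected loss in each arm. It is an overall trigger for adding patients.

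**Conclusion.** The point holds in limited form. HRU over 24 weeks is planned as counts without time at risk, observation can be shorter than 24 weeks, and the same SAP section already handles this for exacerbations. Counts per patient understate 24-week use wherever capture is lost. If loss or its timing differs by arm, the descriptive contrast is distorted.

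With assumed losses of 10% against 15% to 25%, even timing, and equal use in leavers and stayers, the distortion is about 3% to 9%. Larger imbalance or earlier loss gives more (1.21 in the most extreme row), and equal loss gives none in the ratio. These figures rest on assumed arm-specific losses and say nothing about what happened in the trial. No primary or key secondary conclusion is affected.

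**What to change.** In SAP 16.3.3:

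- Report HRU by arm as events per patient-year, beside the counts and the percentage of patients with at least one event.
- For general HRU, end time at risk at the patient's last HRU assessment, up to Week 24. For exacerbation contacts, use the study time already defined in 16.3.3. A single interval ending at the last HRU assessment would discard exacerbation contacts validly recorded later under the reduced options.
- Show by arm how many patients have complete 24-week HRU capture, and state that rates do not correct for informative dropout.
- If the arms are compared, reuse the existing negative binomial model with the matching log-time offset.

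The cost is a short SAP change, one derived observation time for general HRU and a few table rows. The SAP is marked final v1.0 (25 July 2022), so the change would be an SAP amendment. If the protocol is amended for other reasons, reconcile the lists in 7.2.1 to 7.2.3 with the 24-week HRU endpoint. That step needs ethics committee approval (Protocol 11.2) and should not hold up the SAP change, which stands alone.
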